**Exposure to Microplastics in Neonates Receiving Parenteral
Nutrition: A Prospective Cohort Study in Neonatal Intensive Care
Units (Protocol)**

2025.1. 1

1. Background

Microplastics are defined as plastic particles smaller than 5 millimeters in diameter. This definition, established by the National Oceanic and Atmospheric Administration (NOAA), remains the most widely accepted standard. These particles exhibit diverse morphologies, ranging from fragments and fibers to films, granules, and even foam. Due to their minuscule size, they are often referred to as "PM2.5 of the ocean." Microplastics are ubiquitous, present in water bodies, soil, air, and the food chain, with detection reported in seawater, seafood, drinking water, and even honey. Primary microplastics (MPs) originate directly from personal care products, synthetic textiles, and industrial production processes, while secondary microplastics result from the weathering and mechanical degradation of larger plastic products. Recent advancements in analytical techniques have led to the detection of microplastics in human blood, lungs, placentas, and even breast milk, confirming their systemic distribution and potential for accumulation in the human body. These findings have sparked significant public and scientific concern regarding their long-term health impacts, particularly in the most vulnerable population—neonatal infants.

Newborns, particularly those requiring hospitalization due to preterm birth, low birth weight, or severe intestinal dysfunction, are exposed to scenarios markedly different from the general population. In neonatal intensive care units (NICUs), life support and nutritional supply are highly dependent on plastic medical devices such as intravenous infusion bags, tubing, infusion pumps, and ventilator circuits. These devices may contain intentionally added microplastics during production or release secondary microplastics through physical friction or chemical degradation during use. Of particular significance is that for critically ill neonates who cannot be fed orally, parenteral nutrition (PN) serves as their sole source of survival. However, the entire "plastic tubing" system constituting the parenteral nutrition delivery pathway represents a potential, persistent source of microplastic exposure. Studies have demonstrated that microplastic particles can be detected in infusion solutions after passing through plastic equipment^[1]. This implies that neonates receiving intravenous nutrition may be subjected to a unique exposure pattern of "iatrogenic, persistent microplastic infusion."

However, clinical studies on neonatal exposure to AP remain limited. Moreover, most neonatal biomonitoring studies are based on in vitro experiments and random urine samples collected at hospital admission or discharge, without considering the time-dependent nature of exposure. Additionally, there is a lack of research on neonatal microplastic load, particularly quantitative data in blood. Therefore, this study aims to assess the current status of neonatal microplastic exposure during NICU hospitalization. Through a meticulously designed gradient exposure cohort, this study seeks to systematically evaluate and compare the microplastic load in the blood of neonates receiving long-term parenteral nutrition for the first time.

2. Materials and Methods

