2.1. Study Population and Stratification

This study was a prospective observational study. In 2025, 12 neonates were enrolled in the NICU of the Second Affiliated Hospital of Guangdong Province, Jinan University. All

subjects mothers had no underlying conditions such as heart disease, chronic kidney disease, mental illness, hypertension, diabetes, gestational hypertension, or gestational diabetes. Researchers conducted face-to-face interviews to record demographic information. All participants signed informed consent forms and completed questionnaires. A total of 12 neonatal blood samples, 12 breast milk samples, and 12 bottle milk samples were collected. To accurately assess the dose-response relationship between the duration of parenteral nutrition and microplastic load, neonatal blood samples were divided into the following three groups: (1) Long-term exposure group (n=4): Preterm infants requiring total parenteral nutrition support for >14 days due to severe feeding difficulties, necrotizing enterocolitis (NEC), short bowel syndrome, or other serious intestinal diseases. (2) Short-term exposure group (n=4): Preterm infants receiving total parenteral nutrition support for 3 to 7 days due to early adaptation issues (e.g., respiratory distress, transient feeding intolerance) and having successfully transitioned to total enteral nutrition for at least 48 hours prior to blood sample collection. This group represented common, transient, routine iatrogenic exposure in NICUs. Control group (n=4): The cohort consisted of healthy full-term neonates with gestational age \geq 37 weeks. These infants received no intravenous nutritional support or planned fluid therapy, serving as baseline microplastic levels in the absence of relevant iatrogenic exposure. The study strictly adhered to the ethical guidelines of the Declaration of Helsinki, and the protocol was approved by the Medical Ethics Committee of the Second Affiliated Hospital of Guangdong Province, Jinan University.

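### With one blood sample per infant and no pre-PN value described, the study can compare groups but cannot attribute blood load to duration of parenteral nutrition

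*Combined protocol and SAP*

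**What the plan says.** Section 1 (Background) criticises earlier neonatal biomonitoring for relying on in vitro work and on spot urine samples taken on admission or at discharge, "without considering the time-dependent nature of exposure". It then gives this study's aims: to describe current exposure during the NICU stay and to compare blood load in a cohort graded by exposure. It also reports "detection of microplastics in human blood, lungs, placentas, and even breast milk".

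Section 2.1 states that "12 neonates were enrolled in the NICU" and that "A total of 12 neonatal blood samples, 12 breast milk samples, and 12 bottle milk samples were collected". It gives the purpose of the grouping as "To accurately assess the dose-response relationship between the duration of parenteral nutrition and microplastic load". For this, "neonatal blood samples were divided into the following three groups", with 4 infants in each:

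- **Long-term:** preterm, total PN for more than 14 days. No sampling time relative to PN is given.
- **Short-term:** preterm, total PN for 3 to 7 days, sampled after "having successfully transitioned to total enteral nutrition for at least 48 hours prior to blood sample collection".
- **Control:** healthy, gestational age 37 weeks or more, no PN. The section treats this group as supplying the baseline level.

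Section 2.3 (Sample Collection) places the blood draw only as after birth, with no day of life and no reference to PN. Section 2.4 names a correlation test and a Wilcoxon test. It names no paired, change-from-baseline or repeated-measures analysis.

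**The concern.** A dose-response claim about PN duration needs the part of the blood load that came from PN. What is measured is one total per infant: whatever was present at birth, plus whatever was acquired later, less whatever was cleared. Since the Background reports microplastics in placentas, a load before the first infusion has to be considered.

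The only stand-in for a starting value is a different set of infants, and they differ from the PN infants in gestational age and health. If birth load differs between the groups, that difference appears in the results as an effect of PN or of its duration. What is at stake is whether the study may report load acquired from PN, accumulation or a dose-response, or only that groups with different PN histories had different blood loads.

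**Working it through.** **Inputs.** 12 infants, 12 blood samples and three groups of 4 (section 2.1). The sampling times are those in sections 2.1 and 2.3. The documents give no effect size, standard deviation or microplastic concentration, so the check concerns what can be identified, not power.

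**Step 1: reproduce the count.** 4 + 4 + 4 = 12 samples, and 12 / 12 = 1 per infant. The figure in section 2.1 is reproduced. The PN infants number 4 + 4 = 8, and 0 of the 8 have a described pre-PN value.

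**Step 2: write down what each group mean contains.** Let B be the mean birth load (c = control, s = short-term, l = long-term). Let A be the mean net contribution of PN up to the draw, after any clearance.

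- Control mean = Bc
- Short-term mean = Bs + As
- Long-term mean = Bl + Al

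That is three means for five unknowns.

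**Step 3: count what can be separated (rank of the design matrix against number of parameters).**

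| Assumption | Rank | Parameters | Separable? |
|---|---|---|---|
| None | 3 | 5 | No |
| Both preterm groups share one birth load | 3 | 4 | No |
| Controls and both preterm groups share one birth load | 3 | 3 | Yes |
| None, with one pre-PN sample added in each of the 8 PN infants (12 + 8 = 20 samples) | 5 | 5 | Yes |

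The last row is an illustration; the documents describe no such samples.

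**Step 4: see where a difference in birth load goes.**

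- Short-term minus control = As + (Bs − Bc)
- Long-term minus control = Al + (Bl − Bc)
- Long-term minus short-term = (Al − As) + (Bl − Bs)

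Each bracketed birth-load difference enters the contrast one for one. The third contrast avoids the full-term controls and needs only Bl = Bs. It then gives Al − As, but neither A on its own.

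**Step 5: check the sampling times.** As is measured at least 48 hours after the move to full enteral feeding. The interval behind Al is unstated: the draw could have been during PN or after it. The two A terms may therefore allow for clearance differently, even if birth loads were equal. If section 2.3 were taken to mean a draw at birth, before any PN, that single sample would contain no PN contribution. The two sources cannot be separated on either reading.

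The breast milk and bottle milk samples do not help, because neither measures the infant's load at birth.

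**The case against.** The strongest reply is that the design already takes account of exposure time, between infants: no PN, 3 to 7 days, and more than 14 days. Within-infant change would be a different and more demanding design. The aims in section 1, to describe and to compare, need nothing more. This stands. A reader might infer from the Background that the study promises a within-infant time course, but the phrase on time dependence criticises earlier work and is not an aim. Nor does the protocol call its group differences accumulation; that word appears only in general background. The overreach is in the purpose stated in section 2.1.

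A second reply is that birth load varying in the same way in every group adds noise, not bias. This also stands. Bias needs birth load to differ between groups. The documents do not show that it does. They do show that the controls are full-term and healthy while both PN groups are preterm, and they offer no data with which to check equality.

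A third reply is that the controls are the baseline. They are a reference level in other infants, and they replace a pre-PN value only under the equal-birth-load assumption.

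Two further inferences should be resisted. A reader might conclude that every sample was taken after the exposure defining its group. That is explicit only for the short-term group, and the controls had no PN to be sampled after. A reader might also take the Background as reporting microplastics in maternal blood. It says human blood; the case for a load at birth rests on placentas.

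**Conclusion.** The concern holds in a limited form. One sample per infant and no described pre-PN value in any of the 8 PN infants mean that load acquired on PN can be separated from birth load only by assuming equal birth load in full-term controls and both preterm groups. The study cannot test that assumption. The purpose stated in section 2.1 therefore claims more than the design can deliver.

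The conclusion rests on the sample count, on the absence of any described second blood sample, and on birth load being plausible. It does not need birth load to be large. The possible distortion equals the between-group difference in birth load, and the documents give no basis for its size or direction. They also give no basis for stating what share of the variation in blood load comes from birth.

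A reader might go further and call the three-group comparison worthless. The documents do not support that: a descriptive comparison remains valid, and the long-term versus short-term contrast could show an association with duration.

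**What to change.** 1. In section 2.1, restate the purpose as a descriptive cross-sectional comparison of blood microplastic load between groups that differ in PN duration.
2. Report differences as between-infant associations, and not as load acquired from PN, accumulation or dose-response.
3. Describe the controls as a comparison group, not as a pre-exposure baseline.
4. In sections 2.1 and 2.3, record and report each infant's sampling day relative to birth and, for the 8 PN infants, relative to PN start and stop.

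The cost is wording plus a few dates per infant, and a less ambitious claim.

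Pre-PN blood is at most an optional descriptive addition: up to 8 further assays, and only if such blood already exists and met the non-plastic collection rule in section 2.3, which covers the collector as well as the tube. The documents do not show that any exists, and using it might need an ethics or consent change. Values from only some infants would not provide the missing separation for the whole study.

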2.1. Study Population and Stratification

This study was a prospective observational study. In 2025, 12 neonates were enrolled in the NICU of the Second Affiliated Hospital of Guangdong Province, Jinan University. All

subjects mothers had no underlying conditions such as heart disease, chronic kidney disease, mental illness, hypertension, diabetes, gestational hypertension, or gestational diabetes. Researchers conducted face-to-face interviews to record demographic information. All participants signed informed consent forms and completed questionnaires. A total of 12 neonatal blood samples, 12 breast milk samples, and 12 bottle milk samples were collected. To accurately assess the dose-response relationship between the duration of parenteral nutrition and microplastic load, neonatal blood samples were divided into the following three groups: (1) Long-term exposure group (n=4): Preterm infants requiring total parenteral nutrition support for >14 days due to severe feeding difficulties, necrotizing enterocolitis (NEC), short bowel syndrome, or other serious intestinal diseases. (2) Short-term exposure group (n=4): Preterm infants receiving total parenteral nutrition support for 3 to 7 days due to early adaptation issues (e.g., respiratory distress, transient feeding intolerance) and having successfully transitioned to total enteral nutrition for at least 48 hours prior to blood sample collection. This group represented common, transient, routine iatrogenic exposure in NICUs. Control group (n=4): The cohort consisted of healthy full-term neonates with gestational age \geq 37 weeks. These infants received no intravenous nutritional support or planned fluid therapy, serving as baseline microplastic levels in the absence of relevant iatrogenic exposure. The study strictly adhered to the ethical guidelines of the Declaration of Helsinki, and the protocol was approved by the Medical Ethics Committee of the Second Affiliated Hospital of Guangdong Province, Jinan University.

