2.3 Sample Collection

Samples were collected by trained pediatricians and pediatric nurses. After delivery, the newborns blood was drawn using a non-plastic blood collector and then injected into a glass anticoagulation tube (KERONG, 3mL, China Chengdu). Breast milk and milk from bottles were collected by trained nurses or family members and quickly placed into sample boxes. To avoid contamination, all consumables that came into contact with the samples during the sampling process were non-plastic products. All samples were stored in a -80°C environment and strictly anonymized.

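### Postnatal age at blood sampling is not set, matched, listed for collection or adjusted for, and its minimum rises with PN group, so an age effect could pass for a PN dose-response

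*Combined protocol and SAP*

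**What the plan says.** Section 2.1 reports that "In 2025, 12 neonates were enrolled in the NICU" and gives the purpose of the grouping: "To accurately assess the dose-response relationship between the duration of parenteral nutrition and microplastic load". There are 4 infants per group.

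- **Long-term:** "Preterm infants requiring total parenteral nutrition support for >14 days". No sampling day is given.
- **Short-term:** "Preterm infants receiving total parenteral nutrition support for 3 to 7 days", and "having successfully transitioned to total enteral nutrition for at least 48 hours prior to blood sample collection". No upper limit is set on the time to the draw.
- **Control:** healthy term infants without PN, taken as the baseline. No sampling day is given.

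The only timing statement for all blood is in section 2.3 Sample Collection: "After delivery, the newborns blood was drawn using a non-plastic blood collector". Neither the interview items in section 2.2 nor the survey form lists age at the draw. Section 2.4 names group tests, cor.test and wilcox.test, and no model that includes age.

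The Background describes microplastics as present throughout the environment and found in breast milk. It speaks of recent findings as "confirming their systemic distribution and potential for accumulation in the human body", names NICU plastics other than infusion equipment, such as ventilator circuits, and faults earlier neonatal studies for working "without considering the time-dependent nature of exposure".

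**The concern.** An infant cannot have had more days of PN than days of life. A group defined by more PN therefore has a higher minimum age at any draw that follows that PN. Older infants have also had longer contact with every other source that the Background lists. If load rises with age for those reasons, the groups will tend to line up in the order that a PN dose-response would give, and the bias favours the conclusion the study is looking for.

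The control value is affected too. If controls are drawn soon after birth, their load is that of a newborn, not of an infant without PN at the age of the long-term group.

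This is a separate matter from time since the last PN. Infants drawn at the same interval after PN would still differ in age by roughly their PN duration.

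**Working it through.** The plan states no sample-size calculation, effect size or variance, so there is no figure of its own to reproduce.

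**1. Minimum age at the draw (section 2.1).**
- Control: no restriction, so 0 days.
- Short-term: 3 days of PN + 2 days of enteral feeding = 5 days.
- Long-term: more than 14 days, if blood is drawn after the qualifying PN. The plan does not say that it is. An earlier draw, however, would come from an infant who had not yet had the PN that the group label describes, so the dose-response reading needs the later draw.

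**2. What 12 infants can show.** If every load in one group of 4 exceeds every load in another, the exact two-sided Wilcoxon p is 2/C(8,4) = 2/70 = 0.029, below the plan's 0.05. With all three groups completely separated, the rank sums are 10, 26 and 42. Then H = 12/(12 × 13) × (100 + 676 + 1764)/4 − 3 × 13 = 48.85 − 39 = 9.85, and the Kruskal-Wallis p is exp(−9.85/2) = 0.0073. These are noise-free extremes: groups that do not overlap in age need not be separated in load.

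**3. Age-only simulation with zero PN effect.** Load = (1 + slope × age) × log-normal error, with 2,000 runs per setting. The following are assumptions, not figures from the plan:
- slope 0.05, 0.1 or 0.2 of the birth load per day; log-scale SD 0.3 or 0.6;
- PN starting at birth, and long-term infants drawn at the end of 15 to 28 days of PN;
- window A: controls drawn at 0 to 3 days, short-term infants 2 to 4 days after PN;
- window B: controls drawn at 0 to 7 days, short-term infants 2 to 7 days after PN;
- similar ages: all groups at about 15 to 28 days, which places the short-term draw 12 to 21 days after PN.

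Chance alone orders three medians correctly in 1/3! = 1/6 = 17% of runs. Spearman stands in for cor.test, whose method the plan does not name.

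| Setting | Correlation of age and PN days | Control < short < long medians | Kruskal-Wallis p < 0.05 | Spearman p < 0.05 |
|---|---|---|---|---|
| Window A | 0.99 | 52% to 99.6% | 15% to 99.5% | 27% to 100% |
| Window B | 0.98 | 47% to 96% | 13% to 91% | 23% to 98% |
| Similar ages | 0.12 to 0.14 | 15% to 19% | about 4% | 5% to 7% |
| A or B, no age slope | 0.98 to 0.99 | 16% to 17% | 3% to 4% | 5% to 6% |

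The false gradient needs both an age effect and unequal ages. Take away either one and the results return to chance.

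**4. Size of a long-to-short ratio at the age floors (5 and 15 days).** Under the same assumed model it is (1 + 0.05 × 15)/(1 + 0.05 × 5) = 1.75/1.25 = 1.4 at the lowest slope, and (1 + 0.2 × 15)/(1 + 0.2 × 5) = 4/2 = 2.0 at the highest.

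**The case against.** The strongest reply is that the plan fixes only minimum ages. It gives no sampling day for control or long-term infants and no ceiling for short-term infants, so age-matched sampling would comply with it. A reader might infer that the design forces age to rise with group and that the ordering would follow. The documents do not support that: the ordering is possible, not certain. The expected ordering is itself implied by the talk of a gradient and a dose-response; it is not written as a hypothesis.

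Nor do the documents give any rate at which blood load rises over days; the Background speaks only of a potential to accumulate. A reader might take the ratio of the age floors, 15/5 = 3, as the size of the bias. That requires zero load at birth, whereas the Background reports detection in placentas. A non-zero birth load gives the smaller ratios shown in step 4.

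It is also fair to say that absence from a demographic interview does not prove that draw times go unrecorded. The documents are silent on this.

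Finally, postnatal age is not the same as time under NICU devices, and making ages similar would not make device exposure similar.

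All of this limits how strongly the point may be put. It does not remove it: the plan can be followed exactly and still credit PN duration with an age effect.

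**Conclusion.** The concern holds as a gap in design and analysis. Age at the draw is left open, its minimum rises from 0 to 5 to more than 14 days across the groups, and the planned unadjusted tests cannot separate it from PN duration. The last floor rests on the draw following the qualifying PN.

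The direction of the bias, if load does rise with age, is towards a PN dose-response. Its size is unknown. The simulated 47% to 99.6% shows how widely the answer varies with slopes, variances and windows that the plan does not give, and p = 0.029 marks only what 4 versus 4 can reach without noise. Neither figure estimates what this study will find.

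Adjustment by regression would not settle the matter. With 12 infants and age and PN days correlated at 0.98 to 0.99 under the assumed windows, a model could hardly tell them apart.

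**What to change.** 1. Add the date and time of birth and of each blood draw to the data collected.
2. Report each infant's age at the draw beside PN days and load.
3. Where routine sampling allows, draw control and short-term blood at ages that overlap the long-term group. The sampling rules set no upper limit on age. Short-term infants would then be further from their last PN, so report time since PN as well.
4. State in advance that, unless ages at the draw are similar across groups, differences will be reported as PN duration and postnatal age combined, and not as a PN dose-response. Define similar before loads are known, for example as all three groups falling in one common age window. A rule triggered only by non-overlapping age ranges is too weak, because a single overlapping infant would release the claim while age and PN days stayed nearly collinear.
5. Describe the control value as load at the age sampled.

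The cost is two extra data fields, one listing and a conclusion rule, with the possibility of a weaker dose-response claim. No extra blood is needed. The plan is written in the past tense; if the draws have already been made, step 3 is no longer available, and the other steps depend on whether the draw times can be recovered.

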2.2 Interview Content

At enrollment, investigators conducted interviews to collect demographic information from newborns and pregnant women, including education level (high school or below, bachelors degree, masters degree or above), per capita annual income (<100,000 yuan, 100,000-200,000 yuan, >200,000 yuan), occupation (government official, professional technician, general clerk, commercial service, other), number of pregnancies (primipara, multipara), mode of pregnancy (natural delivery, assisted delivery), delivery outcome (preterm, full-term), delivery method (vaginal delivery, cesarean section), newborn gender (male, female), and neonatal weight. Details are provided in Table S1.

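### Neither PN group has a gestational-age or weight band and weeks of gestation are not a listed variable, so immaturity as an explanation for a long versus short PN difference can be examined only crudely, through newborn weight

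*Combined protocol and SAP*

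**What the plan says.** Section 2.1 sets up three groups of 4 to study a dose-response relation between PN duration and microplastic load.

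- **Long-term:** "Preterm infants requiring total parenteral nutrition support for >14 days". The stated reason for PN in this group is worded "due to severe feeding difficulties, necrotizing enterocolitis (NEC), short bowel syndrome, or other serious intestinal diseases".
- **Short-term:** "Preterm infants receiving total parenteral nutrition support for 3 to 7 days". The stated reason for PN in this group is worded "due to early adaptation issues (e.g., respiratory distress, transient feeding intolerance"). These infants must also have been on full enteral feeding for at least 48 hours before blood is drawn.
- **Control:** "healthy full-term neonates with gestational age" of at least 37 weeks. This is the only gestational-age limit in the document.

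Section 2.2 lists the maturity item as "delivery outcome (preterm, full-term") and also lists "newborn gender (male, female), and neonatal weight". The Survey Form after section 2.4 repeats the two-level birth outcome and has a numeric field for newborn weight in kg. Neither list has a field for weeks of gestation.

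Section 2.4 compares baseline characteristics across all three groups by one-way ANOVA, Kruskal-Wallis or Fisher's exact test. It also names the R functions cor.test and wilcox.test. It describes no matching, stratification or adjusted analysis.

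**The concern.** Any contrast with the controls mixes PN with term birth and good health. Long versus short PN is the only contrast made wholly within preterm infants, so a claim about duration leans on it. Yet an infant far below 37 weeks and one just below it qualify equally for either group. It is plausible that infants who stay on total PN beyond 14 days differ in maturity from those who reach full feeds within days.

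Maturity and size could affect load by routes other than PN duration. The background section itself lists other plastic sources in intensive care, such as ventilator circuits, and body size sets the volume in which infused particles are diluted. If the two PN groups differ in maturity, a difference in load could be read as an effect of duration when it is partly or wholly something else. The recorded data would give little help in telling these apart.

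**Working it through.** The plan states no effect size, SD or power, so it has no calculated figure to reproduce. Its group sizes do add up: 4 + 4 + 4 = 12.

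**1. What each recorded variable can show (sections 2.1 and 2.2, Survey Form)**

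- *Preterm/full-term:* by definition all 4 + 4 = 8 PN infants are preterm. The field is constant and carries no information on long versus short.
- *Newborn weight (kg):* this varies and can be tabulated by group. It mixes maturity with fetal growth, and the form does not fix when it is measured. That matters when the groups are defined by more than 14 days versus 3 to 7 days of PN.
- *Gestational age in weeks:* not listed. It must be ascertained to apply the 37-week criterion, but the plan does not make it an analysis variable.

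**2. What the three-group baseline test says about the PN groups**

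Assume every term control weighs more than every PN infant, with no ties. The Kruskal-Wallis statistic is H = [12/(N(N+1))] × Σ(R²/n) − 3(N+1), with N = 12, n = 4 and R the rank sum of each group.

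- *PN groups perfectly balanced:* rank sums 18, 18 and 42 (for example ranks 1, 4, 6, 7 and 2, 3, 5, 8). H = (81 + 81 + 441)/13 − 39 = 7.38. On chi-square with 2 df, p = exp(−7.38/2) = 0.025.
- *PN groups completely separated:* rank sums 10, 26 and 42. H = (25 + 169 + 441)/13 − 39 = 9.85, p = exp(−9.85/2) = 0.007.

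Both results are below 0.05. Under this assumption a significant three-group test is expected from term versus preterm alone and does not tell the reader whether the PN groups are alike.

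**3. What a direct 4 v 4 test of weight could show**

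The smallest two-sided exact Wilcoxon p is 2/C(8,4) = 2/70 = 0.029, reached only with complete separation. The next is 4/70 = 0.057. Power at two-sided 0.05 for a true weight gap of d SD (assumed range, since the documents give none) is as follows. The normal approximation is Φ(d√(4/2) − 1.96). The t-test uses the noncentral t with 6 df and noncentrality d√(4/2). The Wilcoxon figures come from 20,000 simulations of normal data.

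| Gap d (SD) | Normal approximation | t-test | Exact Wilcoxon |
|---|---|---|---|
| 1.0 | 29% | 22% | 14% |
| 1.5 | 56% | 43% | 30% |
| 2.0 | 81% | 66% | 49% |

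A non-significant test would not show that the PN groups were similar.

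**4. How much body size alone could matter**

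Let concentration = particles / (weight × blood volume per kg), with the same blood volume per kg, the same PN duration, and assumed weights of 1.0 and 2.0 kg.

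- *Same particle number infused:* the ratio is (1/1.0)/(1/2.0) = 2.0.
- *Particles proportional to weight:* weight cancels and the ratio is 1.0.

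The documents give no infusion volumes, so the range is 1.0 to 2.0 and no point within it is preferred.

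**The case against.** **Weight is recorded.** A reader might infer that maturity is captured only as preterm or full-term and that imbalance cannot be checked at all. The documents do not support that. Weight is on both lists, and as a continuous baseline variable it falls under the planned comparison. This part of the objection stands: the check is crude, not absent.

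**The form is not the whole data set.** It is an interview form for demographic information. PN duration and indication are not on it either, so clinical data must come from elsewhere, and gestational age must be known to classify the infants. This also stands. The documents support saying that weeks of gestation are not a listed variable, not that they are unavailable.

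**Direction and size are unknown.** A reader might infer that the long-term group must be less mature and that its load is therefore biased upward. Section 2.1 separates the PN groups by duration and indication, not by degree of prematurity, and no figure in the document gives a sign or size. Confounding is plausible but unquantified, and the two-fold ratio is only the upper end of its range.

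**Matching on maturity would not isolate duration.** This is correct. The PN groups also differ in indication, and only the short-term group has a stated enteral period before sampling. That limits what the fix can achieve, but it does not make the maturity gap harmless. A fixed matching window in weeks or per cent of weight would be arbitrary with 4 infants per group at one centre, so none is proposed.

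**Conclusion.** The concern holds in a limited form. Eligibility leaves maturity open in both PN groups, the listed maturity field is constant across all 8 of them, and no matching or adjustment is described. The one graded proxy is weight of unspecified timing. Its planned test includes term controls, and a direct 4 v 4 test would have about 14% to 49% power by exact Wilcoxon for assumed gaps of 1 to 2 SD.

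Immaturity therefore remains a plausible and poorly examined explanation for any long versus short difference. The size of the bias cannot be derived from the documents. The 1.0 to 2.0 concentration ratio rests on assumed weights, equal blood volume per kg, and an unknown relation between infused particles and weight. The point should be acted on because it changes what the study can conclude about duration and costs little to address.

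**What to change.** 1. Replace the preterm/full-term field with gestational age at birth in weeks and days, and state that the weight recorded is birth weight.
2. Tabulate both beside each infant's microplastic load. Compare them between the two PN groups descriptively, not by significance test.
3. When more than one short-term infant is eligible, enrol the one closest in gestational age to a long-term infant.
4. State in section 2.4 that a long versus short difference will not be attributed to PN duration alone. Name the different PN indications, and the short-term group's period of at least 48 hours on enteral nutrition before sampling, as differences that remain unresolved.

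**Cost:** one extra chart item, possibly slightly slower recruitment of the short-term group, and a more cautious dose-response claim. The number of infants and the procedures do not change. If enrolment is already complete, items 1, 2 and 4 can still be done, provided the anonymised samples can be linked to the infants' records.
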